## Statistical Analysis

Data are expressed as mean  $\pm$  SD or as percentages. Statistical analyses will be performed using R 3.2.1 statistical software with RStudio IDE, Version 0.99.467. Paired, two-sided Student's t-test will be used to evaluate the null hypothesis of no difference between baseline and post  $\beta$ -OH-B butyrate protocol.  $p<0.05$  is deemed significant. Pearson's product-moment correlation will be used to examine the relationship between changes in parameters of LV diastolic and systolic function and coronary blood versus changes in myocardial  $\beta$ -OH-B uptake and both univariate and multivariate ANOVA for changes in EF in the 3 different  $\beta$ -OH-B infusion groups.

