## Expected Results

Studies in rodent models of heart failure and in humans with heart failure (31,33,38,39,71,83-86) have demonstrated that ketone utilization by the failing heart is increased. However, no study in humans has examined the effect of exogenous infusion of ketones on myocardial function and myocardial glucose utilization in nondiabetic or type 2 diabetic patients with heart failure. We expect that ketone infusion to elevate the plasma ketone concentration by physiologic (+0.5 mmol/L) and pharmacologic (+2.0 and +5.0 mmol/L) levels will cause a dose-response increase in parameters of LV diastolic/systolic function and a dose-response decrease in glucose utilization ( $^{18}\text{F}$ -2-DOG). Although not measured in the present study, we also would expect increased myocardial  $\beta$ -OH-B uptake to complete with fat oxidation since they share a common intermediate, i.e. acetyl CoA, that feeds into the Krebs Cycle. Because of its favorable P/O ratio and other potential metabolic benefits (17,18), we also expect that multiple parameters of LV diastolic (E/A ratio, diastolic volume, peak LV filling rate), as well as systolic (cardiac index, EF, peak LV ejection rate), function will increase. The present results will allow us to define the plasma  $\beta$ -OH-B concentration at which the substrate's beneficial effects on CV function are observed. We anticipate that elevation of the plasma  $\beta$ -OH-B level to 2.0-5.0 mmol/L, i.e. levels that are observed in 5-10% of individuals treated with SGLT2 inhibitors, will elicit a significant improvement in multiple parameters of LV systolic and diastolic function. If so, the "ketone hypothesis" (17,18) would be supported and explain, at least in part, the beneficial effect of empagliflozin and canagliflozin on hospitalization for heart failure and CV mortality in the EMPA REG OUTCOME and CANVAS studies. If beneficial effects on myocardial function are observed with the low dose  $\beta$ -OH-B infusion (increment in plasma  $\beta$ -OH-B =  $\sim$ 0.5 mmol/L), this will allow the results to be generalized to the great majority of diabetic patients treated with SGLT2 inhibitors. A potential limitation of the present study is the relatively small number of diabetic subjects in each of the three groups. However, given the reproducibility of cardiac MRI and its close agreement with the same parameters derived by echocardiography (76), as well as the reproducibility of the measurement of myocardial  $^{18}\text{F}$ -2-DOG uptake (19), we believe that the sample size (see below) will be sufficient to demonstrate significant effects of  $\beta$ -OH-B infusion on myocardial uptake of glucose, as well as on myocardial function. Lastly, we think that it is possible, although unlikely, that even the highest  $\beta$ -OH-B infusion rate (5.0 mmol/kg.min) may not have any effect on cardiac function even though myocardial  $\beta$ -OH-B uptake is increased and glucose uptake is reduced. If so, this would argue against a role for enhanced myocardial ketone uptake in the CV benefit of empagliflozin and canagliflozin in the EMPA-REG OUTCOME and CANVAS studies (5). Alternatively, it is possible that  $\beta$ -OH-B must be infused for longer than 6 hours to observe its beneficial effects on myocardial function. If the high  $\beta$ -OH-B infusion rate fails to increase parameters of LV function, we are prepared to admit diabetic patients to the CRC for a 72 hour  $\beta$ -OH-B infusion prior to performing the cardiac MRI.

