
## SAMPLE SIZE

Studies in the literature have demonstrated that an increase in 6-minute walk distance of 37 meters is of clinical significance and can be observed with a 10% increase in left ventricular ejection fraction (EF) in patients with Class II-III NYHA (87). In the present study we expect that the baseline EF will be  $45\pm2\%$ . To observe at least a 10% increase in EF with an autocorrelation of 0.96 and an alpha = 0.05 and 90% power following  $\beta$ -OH-B infusion would require 23 subjects per group. With a 10% drop out rate, one needs to recruit 26 subjects per group ([name], Professor, Dept. of Biostatistics and Epidemiology, UTHSCSA).

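### The between-dose comparison of EF change neither adjusts for baseline EF nor uses dose order, although an increasing dose-response is predicted

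*Combined protocol and SAP*

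**What the plan says.** Expected Results predicts that ketone infusion at +0.5, +2.0 and +5.0 mmol/L "will cause a dose-response increase in parameters of LV diastolic/systolic function". It adds that the results will identify the concentration at which benefit appears.

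The Statistical Analysis section gives three tools:
- Within groups: "Paired, two-sided Student's t-test will be used to evaluate the null hypothesis of no difference" between baseline and post-infusion values.
- A Pearson correlation of functional changes with changes in myocardial ketone uptake.
- Between doses: "both univariate and multivariate ANOVA for changes in EF in the 3 different" infusion groups.

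None of these names a baseline covariate, a dose score, a contrast or a post-hoc comparison. What is multivariate about the second ANOVA is not explained.

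Tables 1 and 2 and the Study Protocol schedule a baseline cardiac MRI for every subject before the infusion. Subjects are then split into three groups by a method that is not stated. The only mention of random order concerns the two PET visits in Group II. Groups I and II are infused for 6 hours and Group III for 3 hours.

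**The concern.** An omnibus F test gives the same result if the dose labels are permuted. A significant result says that the groups differ, not that response rises with dose, so the analysis does not address the predicted ordering directly.

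Baseline EF also predicts post-infusion EF. A change score subtracts baseline with a fixed slope of 1, whereas ANCOVA estimates the slope and leaves less residual variance whenever the correlation is below 1. If groups not known to be randomised start at different EFs, the change score also carries any regression to the mean into the group comparison. At stake are some power and clarity on a secondary question. The validity of the trial is not at stake.

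**Working it through.** **Inputs from the plan (Sample Size):** baseline EF 45 with SD 2; "To observe at least a 10% increase in EF with an autocorrelation of 0.96"; "alpha = 0.05 and 90% power following" the infusion; "would require 23 subjects per group"; "With a 10% drop out rate, one needs to recruit 26 subjects per group".

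**The plan's own figure.** SD of change = SD × √(2(1−r)) = 2 × √0.08 = 0.566. A 10% relative increase is 4.5 points, and 4.5/0.566 is about 8 SDs of change. A two-sided paired t-test then needs about 3 subjects, not 23. For 23 to give 90% power, the SD of change must be about 6.4. The dropout step does reproduce: 23/0.9 = 25.6, rounded up to 26, and 3 × 26 = 78. Because r = 0.96 with SD 2 does not lead to 23, I also show assumed values r = 0.8 and r = 0.5, and I express effects in SDs of change.

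**Baseline adjustment.** With equal SDs before and after, Var(change) = 2σ²(1−r) and the ANCOVA residual variance is σ²(1−r²). Their ratio is (1+r)/2, so the reduction is (1−r)/2:
- r = 0.96: 2%
- r = 0.8: 10%
- r = 0.5: 25%

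**Imbalance.** The two group-difference estimates differ by (1−r) × baseline difference. For an assumed 2-point difference this is 0.08 points at r = 0.96 and 1.0 point at r = 0.5.

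**Power of the 2-df test, n = 23 per group.** λ = 23 × Σ(mᵢ − m̄)²/v, with v = 1 for change (66 error df) and v = (1+r)/2 for ANCOVA (65 df). For assumed means 0.1/0.4/1.0, the deviations are −0.4, −0.1 and 0.5, the sum of squares is 0.42 and λ = 9.66, which gives 78.2%. Dividing by 0.98, 0.90 and 0.75 gives λ = 9.86, 10.73 and 12.88.

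**Ordered contrasts.** Linear weights are the doses minus their mean, (−2, −0.5, 2.5). Plateau weights are (−2, 1, 1). Their correlation is 6/√(10.5 × 6) = 0.756, and the joint two-sided 5% critical value is 2.21. The test takes the larger absolute t.

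Power in %, with assumed means for Groups I/II/III:

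| Shape | F on change | F adjusted, r = 0.96 | F adjusted, r = 0.8 | F adjusted, r = 0.5 | Two contrasts, adjusted, r = 0.96 |
|---|---|---|---|---|---|
| Linear 0.1/0.4/1.0 | 78.2 | 79.0 | 82.5 | 89.1 | 83.7 |
| Plateau 0.2/1.0/1.0 | 78.8 | 79.7 | 83.1 | 89.6 | 84.4 |
| High dose only 0/0/0.8 | 78.8 | 79.7 | 83.1 | 89.6 | 78.2 |
| Middle peak 0/0.9/0.4 | 76.8 | 77.6 | 81.2 | 88.0 | 64.2 |
| Middle peak 0/0.9/0 | 87.9 | 88.6 | 91.2 | 95.4 | 40.4 |

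The null rejection rate is about 5% for both tests. The ANCOVA figures ignore the small loss from chance baseline imbalance.

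**Scale.** The linear scenario spans 0.9 SDs of change. That is 0.51 EF points at SD 0.566 and 5.7 points at the back-solved 6.37. With a 4.5-point spread across doses:
- At SD 0.566, both tests have 100% power.
- At SD 6.37 (adjusted at r = 0.96), the F on change has 56.0% and the adjusted two-contrast test 63.2% for a response linear in dose. For a plateau (0, 1, 1) they have 67.6% and 74.4%.

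**The case against.** The strongest reply has four parts.

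1. **The between-dose ANOVA is not the powered comparison.** The trial is sized on the pre/post change within a group, which the paired t-test addresses, and an ANOVA on change has correct type I error. This stands and limits the importance of the point.

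2. **Baseline EF is already used.** A reader might infer that it is thrown away. It is not, because a change score subtracts it. The accurate statement is that it is not adjusted for as a covariate, and at r = 0.96 the difference is negligible. The benefit depends on the true correlation being lower, which is an assumption, although the plan's SD and r do not reproduce its sample size. The undefined multivariate ANOVA might have been meant to include covariates, and the plan should say so.

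3. **An ordered contrast is a trade-off.** It gains for linear and plateau shapes, gives no advantage for a high-dose-only step and loses badly for a middle peak. A weaker top-dose response cannot be excluded: Group III is infused for half as long, and Expected Results allows that longer infusion may be needed to see benefit. This stands, so the contrast should not replace the F test.

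4. **Dose and duration are mixed in Group III.** No contrast removes this. Leaving Group III out is costly: the adjusted Group I versus II comparison has about 17% power in the linear scenario and 76% in the plateau one.

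A reader might also infer that a trend test was considered and rejected. The documents do not mention one.

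**Conclusion.** The point holds as a modest improvement to the analysis. The plan predicts an ordered response but names only an unordered comparison, without baseline adjustment and with one undefined term.

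Adjustment adds under 1 point of power to the 2-df test at r = 0.96, about 4 points at an assumed r = 0.8 and about 11 at an assumed r = 0.5 in the linear and plateau scenarios. The ordered contrast adds about 5 points beyond the unadjusted F for those shapes at r = 0.96, nearly all from using dose order.

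These figures assume 23 evaluable subjects per group, equal SDs before and after, and effects small enough relative to the SD of change that power is below 100%. Here a plateau means one reached by +2 mmol/L. If it were already reached at +0.5 mmol/L, the groups would not differ and neither test would have power to detect a dose effect.

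A reader might infer that ANCOVA repairs allocation that was not randomised. It does not: it adjusts for measured baseline EF only, and with pre-existing group differences ANCOVA and change scores can answer different questions. The Study Protocol's 19 per group conflicts with the 23 and 26 in Sample Size and must be reconciled, but the comparison of methods hardly changes at 19 or 26.

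**What to change.** Before the analysis, amend the Statistical Analysis section as follows:
- Fit post-infusion EF on baseline EF and dose group (ANCOVA), and keep the 2-df group test as the between-dose comparison.
- From the same model, add a prespecified ordered contrast as a supporting analysis of the dose-response hypothesis. One option is the larger of a linear and a plateau contrast at a joint two-sided 0.05. State that it is weak if the middle dose responds most.
- State that any contrast using Group III mixes dose with a 3-hour rather than 6-hour infusion, and interpret it accordingly.
- State how subjects are allocated to the three groups.
- Define multivariate ANOVA: which outcomes or covariates it contains and what it tests.

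The cost is SAP wording, a few lines of R and one error degree of freedom. No extra subjects, visits or measurements are needed. Because the 2-df test is kept, protection against an unexpected dose shape is not lost.

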Currently, it is not known what plasma  $\beta$ -OH-B level is required to observe an improvement in LV diastolic/systolic function. Based upon the study of Gormesen et al (70), we anticipate that an increase in plasma  $\beta$ -OH-B of ~2 mmol/L will be adequate to augment myocardial  $\beta$ -OH-B uptake sufficiently to switch the myocardium from glucose to ketone utilization and result in an improvement in cardiac function. Therefore, subjects in GROUP II will be studied on two occasions with NaHCO3 infusion to serve as time controls. Since we previously have shown that Na- The total volume of  $\beta$ -OH-B and NaHCO3 to be infused will be the same to obviate any effect of volume on cardiac function. Blood glucose and electrolytes will be monitored similarly as described above for  $\beta$ -OH-B infusion. As mentioned above, the volume will not exceed 300 ml to avoid volume overload. We are unaware of any evidence that the NaHCO3 infusion has any effect on cardiac function. We have not included a time control study for the low and high dose B-OH-B infusion studies although, depending

upon the results with the lower and higher B-OH-B infusions, we may choose to perform the control NaHCO3 infusion in these groups as well.

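### The planned EF tests never use Group II's NaHCO3 session, so the pre-post changes and the gradient across dose groups cannot by themselves support a ketone-specific dose-response or threshold

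*Combined protocol and SAP*

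**What the plan says.** **Tests.** Under Statistical Analysis, "Paired, two-sided Student's t-test will be used to evaluate the null hypothesis of no difference between baseline and post" β-OH-B infusion. The between-group analysis is "both univariate and multivariate ANOVA for changes in EF in the 3 different" infusion groups. A Pearson correlation is also planned. No contrast with NaHCO3 is named, and no adjustment for volume, cation or infusion duration.

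**Conclusions intended.** Expected Results predicts that raising ketones to the three levels "will cause a dose-response increase in parameters of LV diastolic/systolic function". It also says the study will define the plasma β-OH-B "concentration at which the substrate's beneficial effects on CV function are observed", and that improvement at 2.0-5.0 mmol/L would support the ketone hypothesis.

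**Control.** Study Protocol (Experimental Design) gives Group II a NaHCO3 session as a time control. The volumes of the two infusions are "to be infused will be the same to obviate any effect of volume on cardiac function". Table 2 gives the control as 0.12 M and schedules a baseline and a post-infusion cardiac MRI at both sessions. Groups I and III have no such session in the plan: "We have not included a time control study for the low and high dose B-OH-B infusion studies". The option of adding one later is kept open and tied to what is seen: "upon the results with the lower and higher B-OH-B infusions, we may choose to perform the control". Study Protocol adds that the investigators know of no evidence that NaHCO3 affects cardiac function, and that "the volume will not exceed 300 ml to avoid volume overload".

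**The concern.** The design recognises time and volume as rival explanations and schedules a session to remove them in Group II, but the analysis plan does not use that session. A pre-post change in any group therefore contains whatever passing time, infused volume and accompanying cation do to EF, as well as any ketone effect.

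The ANOVA of change does not solve this. Groups I and II are scanned at the same time, so a common time effect cancels between them. Volume and cation do not cancel, because they rise with dose. Group III differs in scan time as well.

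The stakes run both ways. If load raises EF, part of a gradient would be credited to ketones. If load lowers EF, a real benefit at the highest dose could be hidden, and Expected Results would read a null result there as evidence against the ketone mechanism.

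**Working it through.** The plan gives no figure for load, so this is a direct calculation from its infusion schedule.

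**Inputs from the documents**
- Infusate: 100 mg/mL (Study Protocol), given as 0.8 M in Table 1; the same solution for all groups.
- Rates (Study Protocol), 20-minute prime then constant: I 0.4 then 0.2; II 1.5 then 0.75; III 4.0 then 2.0 mg/kg/min.
- Repeat MRI starts after 5 h (300 min) in I and II, and after 2 h (120 min) in III.
- Control: 0.12 M NaHCO3, same volume as β-OH-B, Group II only (Table 2).

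**Assumptions**
- The salt of the study infusate is not named in the visible text. I assume one cation per β-OH-B ion, at 0.8 mmol/mL.
- The infusion runs at the stated rate until any volume limit is reached.

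**Formulas**
- Dose at MRI start (mg/kg) = prime × 20 + rate × (T − 20)
- Volume (mL/kg) = dose / 100
- Cation (mmol/kg) = volume × 0.8

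| Group | Dose at MRI start, mg/kg | Volume, mL/kg | Cation, mmol/kg |
|---|---|---|---|
| I | 0.4×20 + 0.2×280 = 64 | 0.64 | 0.512 |
| II | 1.5×20 + 0.75×280 = 240 | 2.40 | 1.92 |
| III | 4.0×20 + 2.0×100 = 280 | 2.80 | 2.24 |
| II, NaHCO3 | volume matched | 2.40 | 2.40×0.12 = 0.288 |

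**Ratios at MRI start**
- I to II: 2.40/0.64 = 3.75, beside a ketone target that rises 2.0/0.5 = 4-fold.
- I to III: 2.80/0.64 = 4.4 (target 5.0/0.5 = 10-fold).
- II to III: 2.80/2.40 = 1.17 (target 5.0/2.0 = 2.5-fold). Here the constant rate differs 2.0/0.75 = 2.7-fold, and scan time is 2 h against 5 h.

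**What the control covers.** Its volume is the same as Group II's. Group I receives 0.64/2.40 = 27% of it and Group III 117%. Its cation load is 1.92/0.288 = 6.7 times below Group II's, and also below Group I's 0.512 mmol/kg. If 100 mg/mL means the sodium salt (about 0.79 M) or the free acid (about 0.96 M), the 6.7 becomes 6.6 or 8.0.

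**Volume limit.** At MRI start 300 mL is reached only above 300/2.80 = 107 kg in Group III and 300/2.40 = 125 kg in Group II. Below 107 kg the ratios do not depend on weight. If rates were instead lowered in advance to keep the whole infusion under 300 mL, Group III's load at MRI start would be smaller in heavier subjects.

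**The case against.** The strongest reply has four parts.

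1. *The control sits where the main claim sits.* The protocol expects the effect at about 2 mmol/L and gives that group the volume-matched session. This stands, and it is why the remedy is cheap. But a control that no test uses does not protect the result.

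2. *The cation argument is weak.* The salt is unnamed, a sentence in Study Protocol that may explain the choice of NaHCO3 breaks off, and rows of Table 2 are cut. This stands in part. A reader might infer that the 0.12 M control was chosen wrongly or without reason; the documents do not support that, since the rationale may be in lost text. What can be said is that 0.12 M at equal volume does not match about 0.8 M in cation. The statement that NaHCO3 has no known cardiac effect does not settle the effect of the larger β-OH-B cation load.

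3. *No effect of load on EF is shown.* This stands. At an assumed 70 kg the volumes at MRI start are about 45, 168 and 196 mL. The protocol treats volume overload as a hazard and cites lower preload as a possible benefit, which if anything points away from a false gain. Neither remark fixes the direction for EF.

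4. *Exposure is uneven.* This also stands. Cumulative load hardly differs between II and III, and a benefit in Group I would occur at the lowest load. The concern is mainly with the I-to-II and I-to-III comparisons and with all uncontrolled pre-post tests.

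**Conclusion.** The concern holds as a question of attribution. The two planned EF analyses leave time, volume and probably cation effects in the estimate, while the conclusions in Expected Results are specific to ketones. Volume at MRI start rises 3.75-fold from Group I to II and 4.4-fold from I to III. These figures rest on the stated rates, concentration and scan times; the cation figures also rest on the assumed 1:1 counter-cation at about 0.8 M.

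Two stronger readings should be resisted. A reader might infer that an EF gradient would be spurious or biased upward. The documents give no EF effect of this load, so they show neither its size nor its sign. A reader might also infer that the study is uncontrolled or needs a new control solution. It has a usable time-and-volume control in Group II. A 0.8 M cation-matched infusion would be a safety trade-off in heart failure and is not needed for the correction below.

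This is an inexpensive improvement to the analysis and its interpretation.

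**What to change.** **Statistical Analysis.** Name as the controlled EF test the within-subject Group II contrast (post minus pre with β-OH-B) minus (post minus pre with NaHCO3), by two-sided paired t-test. State that it controls for time and infused volume but, as far as the visible text shows (0.12 M against about 0.8 M), not for cation.

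**Expected Results.** Describe any gradient across Groups I to III as a response to infusion dose. Do not claim a ketone-specific dose-response or threshold concentration from the pre-post tests or from the I-to-II or I-to-III comparison.

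**Presentation.** The Group II NaHCO3 change may be shown beside the Group I and III changes, descriptively only. Note that Group III is scanned at 2 h, is infused 2.7 times faster than Group II and has received 17% more volume by then; that Group I receives 27% of the control volume; and that random allocation to dose group is not stated.

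**Cost.** No added subjects, infusions or scans, since both Group II MRI sessions are already scheduled. The dose-response and threshold claims become more conditional. The contrast may also be less precise than a simple pre-post change: with equal variances its SD is √(2(1−r)) times that of one session's change, where r is the correlation between the two changes. That is √2 times if r = 0, and no larger than the pre-post SD once r reaches 0.5. The documents do not give r.

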## Expected Results

Studies in rodent models of heart failure and in humans with heart failure (31,33,38,39,71,83-86) have demonstrated that ketone utilization by the failing heart is increased. However, no study in humans has examined the effect of exogenous infusion of ketones on myocardial function and myocardial glucose utilization in nondiabetic or type 2 diabetic patients with heart failure. We expect that ketone infusion to elevate the plasma ketone concentration by physiologic (+0.5 mmol/L) and pharmacologic (+2.0 and +5.0 mmol/L) levels will cause a dose-response increase in parameters of LV diastolic/systolic function and a dose-response decrease in glucose utilization ( $^{18}\text{F}$ -2-DOG). Although not measured in the present study, we also would expect increased myocardial  $\beta$ -OH-B uptake to complete with fat oxidation since they share a common intermediate, i.e. acetyl CoA, that feeds into the Krebs Cycle. Because of its favorable P/O ratio and other potential metabolic benefits (17,18), we also expect that multiple parameters of LV diastolic (E/A ratio, diastolic volume, peak LV filling rate), as well as systolic (cardiac index, EF, peak LV ejection rate), function will increase. The present results will allow us to define the plasma  $\beta$ -OH-B concentration at which the substrate's beneficial effects on CV function are observed. We anticipate that elevation of the plasma  $\beta$ -OH-B level to 2.0-5.0 mmol/L, i.e. levels that are observed in 5-10% of individuals treated with SGLT2 inhibitors, will elicit a significant improvement in multiple parameters of LV systolic and diastolic function. If so, the "ketone hypothesis" (17,18) would be supported and explain, at least in part, the beneficial effect of empagliflozin and canagliflozin on hospitalization for heart failure and CV mortality in the EMPA REG OUTCOME and CANVAS studies. If beneficial effects on myocardial function are observed with the low dose  $\beta$ -OH-B infusion (increment in plasma  $\beta$ -OH-B =  $\sim$ 0.5 mmol/L), this will allow the results to be generalized to the great majority of diabetic patients treated with SGLT2 inhibitors. A potential limitation of the present study is the relatively small number of diabetic subjects in each of the three groups. However, given the reproducibility of cardiac MRI and its close agreement with the same parameters derived by echocardiography (76), as well as the reproducibility of the measurement of myocardial  $^{18}\text{F}$ -2-DOG uptake (19), we believe that the sample size (see below) will be sufficient to demonstrate significant effects of  $\beta$ -OH-B infusion on myocardial uptake of glucose, as well as on myocardial function. Lastly, we think that it is possible, although unlikely, that even the highest  $\beta$ -OH-B infusion rate (5.0 mmol/kg.min) may not have any effect on cardiac function even though myocardial  $\beta$ -OH-B uptake is increased and glucose uptake is reduced. If so, this would argue against a role for enhanced myocardial ketone uptake in the CV benefit of empagliflozin and canagliflozin in the EMPA-REG OUTCOME and CANVAS studies (5). Alternatively, it is possible that  $\beta$ -OH-B must be infused for longer than 6 hours to observe its beneficial effects on myocardial function. If the high  $\beta$ -OH-B infusion rate fails to increase parameters of LV function, we are prepared to admit diabetic patients to the CRC for a 72 hour  $\beta$ -OH-B infusion prior to performing the cardiac MRI.
